1.0 Research Design

1.1 Purpose/Specific Aims

The purpose of this study is to explore the efficacy of Azithromycin and Hydroxychloroquine in patients with proven SARS-CoV-2 infection with symptoms consistent with COVID-19.

A. Objectives

Primary Objective:

Determine change in viral load at day 6 compared to baseline between two regimens to treat COVID-19 and a contemporaneous control group.

Secondary Objective:

- Time to resolution of symptoms (symptom questionnaire)
- Change in the fever curve resulting in shorter time to afebrile for 48 hours
- Normalization of vital signs
- Time to discharge (if hospitalized)
- Assessment of agent toxicity as measured by standard metrics
- Collection of throat swabs and blood for viral load, presence of IgM or IgG antibodies
- If feasible on samples collected for quantitative PCR decrease in virus shedding (in oropharyngeal secretions)
- Measures of cytokines in blood including IL6, IL-8, TNF, INF
- Routine standard of care labs obtained as part of the care of these patients such as differential white count, CRP, troponin and LFTs will be analyzed for correlative trends

B. Hypotheses / Research Question(s)

[figure not shown]
We propose performing a three-arm randomized trial comparing the efficacy of single agent hydroxychloroquine to the combination of hydroxychloroquine and azithromycin, and to a delayed hydroxychloroquine regimen, which will serve as a contemporaneous Day 1-6 placebo control, in eliminating detectable SARS-CoV-2 on day 6 following the initiation of treatment in order to determine which regimen is more effective.

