A group in France [9] has recently reported on a completed clinical study substituting hydroxychloroquine (an analogue of chloroquine), which has been shown to have an anti-SARS-CoV (agent of SARS in 2002) activity in vitro [10] a virus sharing significant homology with SARS-CoV-2. There is strong evidence that the safety profile of hydroxychloroquine is better than that of chloroquine allowing higher daily dosing [11] and fewer drug-drug interactions [12-16]. In this study, a total of 26 COVID-19 patients were included in a single arm trial receiving 600mg of hydroxychloroquine po daily and their viral load in nasopharyngeal swabs was tested daily in a hospital setting. Depending on their clinical presentation, azithromycin was also added to the treatment. Sixteen untreated patients from a second center and cases refusing to participate in the protocol were included as controls. Presence and absence of virus at Day 6-post inclusion was considered the end point. Six patients were asymptomatic, 22 had upper respiratory tract infection symptoms and eight had lower respiratory tract infection symptoms. Twenty cases were treated in this study and showed a significant reduction of the viral carriage at day six-post inclusion compared to controls, and much lower average duration of viral carriage than that reported in the untreated patients. Of those receiving hydroxychloroquine alone, 8/14 had no evidence of virus at day six. Azithromycin [17-19] added to hydroxychloroquine was significantly more efficient for virus elimination with 0/6 patients with detectable virus on day six [9]. Based on these results we propose performing a three-arm randomized trial comparing the efficacy of single agent hydroxychloroquine to the combination of hydroxychloroquine and azithromycin as well as to a group receiving a placebo, where initiation of hydroxychloroquine treatment may begin after viral sampling on day 6. The primary endpoint in this study is a measure of success in eliminating detectable SARS-CoV-2 on day 6 following the initiation of treatment (or in the case of delayed hydroxychloroguine. the initiation of supportive care). Secondary endpoints will address questions surrounding clinical and biologic endpoints. This trial is needed in order to determine if the addition of azithromycin to hydroxychloroquine is superior in reducing viral load to hydroxychloroquine alone. At present, hydroxychloroquine is one of only a handful of agents that have shown some promise in treating COVID-19. Determining the activity of azithromycin in combination with hydroxychloroquine would be of benefit by either discovering there is improved activity, or by determining that there is little or no improvement in activity and therefore spare the logistics and expense of adding azithromycin to the regimen. The use of a short-term placebo arm where the initiation of hydroxychloroquine can begin following day 6 virus level sample collection will allow hydroxychloroquine treatment and a placebo treatment arm to be compared. This study will also provide a significant opportunity to learn more about COVID-19 and SARS-CoV-2 through the completion of the studies supporting the secondary endpoints.

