
Vital Signs

Temperature will be obtained four times a day (first thing in AM, mid-day, PM, and bedtime). Significant abnormalities will be recorded as an AE. Body temperature will be measured in degrees Fahrenheit using an automated thermometer which will be provided to the patient.

5. Study Efficacy/Response Assessments

Quantitative PCR measurements of viral load at baseline, Day 3 and Day 6. Day 6
measurement compared to baseline will serve as the study endpoint. Other response
criteria used as secondary endpoints include change in temperature curve over time,
change in measured cytokines (IL6) and improvement in clinical symptoms as
determined by clinician assessment and patient questionnaire.

D. Data Points

Case Report Forms

Completion of the electronic case report forms (eCRFs) will be done in accordance with the instructions outlined in the study specific data capture plan. All eCRFs are considered the primary data collection document for the study and are stored in OnCore® in a confidential format. Only key personnel who are delegated in the delegation of authority log are permitted to make entries,

changes, or corrections in the eCRF. All users of OnCore® will complete user training, as required or appropriate per regulations. An audit trail will be maintained automatically by the electronic CRF management system.

Data Points to be collected:

- · Baseline medical history
- Treatment compliance
- Daily temperatures
- Symptoms of disease
- Adverse events
- Concomitant medications
- Any standard of care treatments or procedures to manage COVID-19

Data Submission Timeline and Forms

Completion of eCRFs will occur within 72 hours of study time point unless otherwise indicated. Baseline (pre-study) eCRFs (e.g., enrollment, medical history, concomitant medications, etc.) will be completed no later than 24 hours after the start of treatment.

E. Study Duration

Study participants will be treated for ten (10) days and will then remain on follow-up for up to 6 months after the completion of treatment. The estimated time to complete the entire study is 8 months (November 2020).

We will account for all the patients registered in the study. The number of patients who were not evaluable, who died or withdrew before treatment was completed will be specified. The distribution of follow-up time will be described and the number of patients lost to follow-up will be given.

F. Endpoints

Primary endpoint:

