 Change in viral load at day six compared to baseline between hydroxychloroquine sulfate alone and hydroxycholorquine sulfate plus azithromycin to treat COVID-19. A second concurrent comparison will evaluate change in viral load at day 6 between hydroxychloroquine sulfate alone and a placebo.

Secondary endpoints (descriptive, not driving statistics):

- 1. Time to resolution of symptoms (symptom questionnaire)
- 2. Change in the fever curve resulting in shorter time to afebrile for 48 hours
- 3. Improvement in vital signs
- 4. Time to discharge (if hospitalized)
- 5. Time to recovery (back to work, school etc...)
- 6. Assessment of agent toxicity as measured by standard metrics
- 7. Collection of oropharynx swab and blood for viral load and microbiome analysis
- 8. Decrease in virus shedding (in nasopharyngeal secretions) and serology
- 9. Measures of cytokines in blood including IL6, IL8, TNF and INF
- 10. Measures of inflammatory markers such as ferritin, D-Dimer, CRP, Troponin and LDH

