1.5 Sample Size Justification

Randomized clinical trial comparing hydroxychloroquine with or without azithromycin in patients with the COVID-19 disease, with the addition of a third arm with a placebo and delayed hydroxychloroquine. Here we follow Gautret et al. [9] in using, as a primary endpoint, absence of viral evidence of disease six days following start of treatment. In that study (Table 3 of ref 9), there were 14 patients treated with hydroxychloroquine alone, and 8/14 (57.1 percent) of them were virus-free at 6 days. There were six patients treated with both hydroxychloroquine plus azithromycin, and all six (100%) were virus-free at 6 days. In a third group of patients with no hydroxychloroquine, there were 16 patients, of whom 2 (12.5 percent) were virus-free at 6 days. We propose a three-arm trial as follows: Arm 1 (HCQ + AZ), Arm 2 (HCQ alone), and Arm 3 (delayed HCQ), with patients randomized 2:2:1.

The primary outcome is a comparison of Arm 1 to Arm 2, with the aim of determining if the addition of AZ is effective. Using the proportion of patients that are virus-free at 6 days as the primary endpoint of the study, and assuming that the proportion of patients in the hydroxychloroquine arm who are virus free at 6 days is 0.571, the following table shows the detectable proportion virus-free in the combination arm with 80% power. These samples sizes are with a 5% level two-sided test of proportions.

Proportion virus-free HCQ only	Proportion virus-free HCQ plus AZ	Proportion difference	Patients per rm
0.571	0.821	0.250	52
0.571	0.805	0.234	60
0.571	0.771	0.200	85
0.571	0.721	0.150	158

For example, if we enroll 60 patients per arm, we could detect, with 80% power, an increase in the proportion of virus-free patients from 57.1% in the hydroxychloroquine arm to 80.5% in the combination arm.

The two-sided Type I error probability associated with this test is 0.05. We will use an uncorrected chisquared statistic to evaluate this null hypothesis.

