A second, independent goal of the study is to ensure that, in fact, hydroxychloroquine is effective in reducing viral load. Thus, we plan a third, control arm, in which patients will receive a placebo for six days, at which time they will switch to receiving HCQ. We plan to compare Arms 2 and 3, with the control (Arm 3) having half the sample size of Arm 2. Based on the Gautret et al. study, we assume the baseline proportion of patients who are virus-free at six days is 0.125. The following table shows the detectable difference with a variety of baseline rates:

Proportion virus-free HCQ only	Proportion virus-free HCQ plus AZ	Proportion difference	Patients per rm
-----------------------------------	--------------------------------------	-----------------------	-----------------

ne for Treatment of

Confirmed COVID-19

Protocol Version Date: 08-May-2020

0.125	0.401	0.276	60
0.150	0.434	0.280	60
0.200	0.497	0.290	60
0.250	0.554	0.304	60

Thus, for a range of plausible virus-free rates for the control arm, the detectable rate for the HCQ arm is well within the range reported by Gautret et al. [9]. With this three-arm study, we will need 60 patients in each of the first two arms and 30 in the control arm, for 150 in total.

A key secondary endpoint will be the number of days from initiation of therapy to VND (virtually no disease). This can be displayed graphically using Kaplan-Meier survival curves, and formally assessed using a log-rank test. Other secondary endpoints that can be assessed in this way are (1) Time in days to being afebrile for 48 hours, (2) time in days to resolution of symptoms (as assessed by a symptom questionnaire), (3) time in days to discharge (if hospitalized), and (4) time to recovery (able to return to work or school). Other measures that will be assessed via descriptive statistics are agent toxicity and improvement over time in vital signs.

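### The protocol defines the primary endpoint two ways, change in viral load and virus-free status at Day 6, and only the second has a test and a power calculation

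*Protocol*

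**What the plan says.** Three places in the protocol make the endpoint a change from baseline:

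- 1.1.A, Primary Objective: "Determine change in viral load at day 6 compared to baseline between two regimens".
- 1.3.C.5, Study Efficacy/Response Assessments, on the Day 6 quantitative PCR: "measurement compared to baseline will serve as the study endpoint". The sentence after it lists the secondary endpoints as something separate.
- 1.3.F, under the primary endpoint heading: "Change in viral load at day six compared to baseline between hydroxychloroquine sulfate alone" and the combination. For Arm 2 vs Arm 3 it adds: "A second concurrent comparison will evaluate change in viral load at day 6 between hydroxychloroquine sulfate alone and a placebo".

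Four places use clearance of detectable virus:

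- Protocol 1.1.B, the research question: "in eliminating detectable SARS-CoV-2 on day 6 following the initiation of treatment in order to determine which regimen is more effective".
- Protocol 1.2: "The primary endpoint in this study is a measure of success in eliminating detectable SARS-CoV-2 on day 6".
- Protocol 1.5, where Arm 1 vs Arm 2 is sized: "Using the proportion of patients that are virus-free at 6 days as the primary" endpoint. Arm 2 vs Arm 3 is sized on the same scale: "we assume the baseline proportion of patients who are virus-free at six days is 0.125".
- SAP 6.1, which names the Day 6 virus-free proportion as primary and tests it with an uncorrected chi-squared statistic at two-sided 0.05.

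**The concern.** The two definitions can classify the same patient differently. A patient whose load falls a long way but stays detectable does well on the first and fails on the second. A patient with a low starting load who becomes undetectable succeeds on the second and shows only a small change on the first.

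A reader of 1.3.F and a reader of 1.5 or SAP 6.1 would therefore expect different primary results. Protocol 1.8 places specimen analysis at the end of the study or accrual period, so both results would become available together. The 80% power applies to one definition only. The 5% error rate holds only if the choice between them is fixed beforehand.

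The specimen that decides the primary endpoint is also not named. Oropharynx swab, saliva and blood are all collected at Day 6 (1.3.A and 1.8), so virus-free status is incompletely defined.

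**Working it through.** **1. What each definition has behind it**

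| Element | Virus-free at Day 6 | Change in viral load |
|---|---|---|
| Test | Uncorrected chi-squared (1.5, SAP 6.1) | None |
| Assumed effect | 0.571 vs 0.805; 0.125 vs 0.401 | None |
| SD, scale, detection-limit rule | Scale and SD not needed | None |
| Power | Tables in 1.5 and SAP 6.1 | None |
| Futility rule | Conditional power, simulated (SAP 6.1) | None |
| Covariate model | Logistic regression (SAP 6.1) | None |

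Change in viral load otherwise appears only in the list of outcome variables in 1.6.

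**2. Reproducing the stated power (virus-free proportion)**

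Inputs from 1.5 and SAP 6.1: two-sided alpha 0.05, 60/60/30 patients, and the rates above. With p̄ the pooled rate:

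Power = Φ{ [|p₂ − p₁| − 1.96·√(p̄(1−p̄)(1/n₁+1/n₂))] / √(p₁(1−p₁)/n₁ + p₂(1−p₂)/n₂) }

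- Arm 1 vs Arm 2: p̄ = (0.571 + 0.805)/2 = 0.688. The pooled SE is 0.0846 and the unpooled SE 0.0818. Then (0.234 − 1.96 × 0.0846)/0.0818 ≈ 0.83, giving power 0.798 (stated 0.800). Exact binomial power is 0.808.
- Arm 2 vs Arm 3: p̄ = (30 × 0.125 + 60 × 0.401)/90 = 0.309. The pooled SE is 0.1033 and the unpooled SE 0.0875. Then (0.276 − 1.96 × 0.1033)/0.0875 ≈ 0.84, giving power 0.800 (stated 0.800). Exact power is 0.809.
- The sample sizes in the first table of 1.5 come out as 52, 61, 86 and 159 per arm, against 52, 60, 85 and 158 stated.

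The planned size therefore rests wholly on the binary endpoint.

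**3. Change in viral load**

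Power cannot be computed from the documents. What the planned arms could detect, in SD units with complete normal data, is (1.960 + 0.842)·√(1/n₁ + 1/n₂):

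- 60 vs 60: 2.802 × 0.1826 = 0.51 SD
- 60 vs 30: 2.802 × 0.2236 = 0.63 SD

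No target difference is given to set against these.

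**4. Illustration (assumptions, not document figures)**

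Assume normal log10 load, a baseline–Day 6 correlation of 0.3 to 0.7, and a Day 6 SD of 1 to 3 times the baseline SD. Day 6 values below the limit are set to the limit, and the limit is placed so that 57.1% and 80.5% are undetectable. With 60 per arm and 20,000 simulated trials per setting, power of a t-test on raw change is:

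| SD ratio | corr. 0.3 | corr. 0.5 | corr. 0.7 |
|---|---|---|---|
| 1 | 0.21 | 0.23 | 0.26 |
| 1.5 | 0.35 | 0.42 | 0.49 |
| 2 | 0.49 | 0.58 | 0.69 |
| 3 | 0.66 | 0.75 | 0.85 |

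Analysing Day 6 load adjusted for baseline gives 0.79 to 0.89 throughout.

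With no effect (0.571 in both arms), the chance of at least one p < 0.05 is:

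- proportion or raw change: 0.093 to 0.103
- proportion or baseline-adjusted load: 0.085 to 0.097
- one pre-specified test: about 0.05

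**The case against.** The strongest reply is that the analysis section is consistent. SAP 6.1 names one endpoint and one test, builds its power tables and futility rule on that endpoint, and plans logistic regression in terms that treat the primary outcome as binary. An analyst who follows it has a single primary analysis. The inflated error rate arises only if someone sets that text aside after seeing the data and substitutes an analysis that the documents do not describe. The documents also use viral load loosely: 1.5 and SAP 6.1 state the Arm 2 vs Arm 3 goal as a reduction in viral load and then power it on proportions. The wording in 1.3.C.5 taken alone could cover clearance.

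Most of this is fair, and it is the reason to adopt the SAP definition. It does not remove the conflict. Loose usage cannot explain 1.3.F, the protocol's own endpoint section, which says change from baseline outright. Neither document states that the SAP prevails. The error-rate figures are conditional and are not the plan's error rate.

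On the specimen, 1.1.A and 1.3.F link viral load to swab and blood, but only in secondary items, and 1.8 lists the viral load assay for the research samples in general. The deciding specimen remains unstated, although a laboratory manual that is not part of these documents may name it.

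It is also fair that a detailed model for change in viral load is not needed to resolve the conflict, since 1.3.F treats secondary endpoints as descriptive.

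**Conclusion.** The concern holds and must be fixed. Protocol 1.3.F, with 1.1.A and 1.3.C.5, names a different primary variable from 1.1.B, 1.2, 1.5 and SAP 6.1, and the split covers both comparisons. This rests on the text alone.

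The stated 80% power is sound for the virus-free proportion and cannot be claimed for change in viral load, whose power is unknown. The illustration suggests it could be lower than, similar to or higher than 0.80 (0.21 to 0.89 depending on method and assumptions). A free choice between the two endpoints would bring the false-positive rate to about 0.085 to 0.103. Both of these ranges depend on the assumed correlation, SD ratio and handling of undetectable values.

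**What to change.** 1. In 1.1.A, 1.3.C.5 and 1.3.F, name the proportion of patients with no detectable SARS-CoV-2 at Day 6 as the primary endpoint for Arm 1 vs Arm 2, and use the same endpoint for Arm 2 vs Arm 3. This matches 1.5 and SAP 6.1.
2. In 1.3.F and SAP 6.1, add one sentence naming the single specimen that determines it, for example the oropharynx swab, for the sponsor to confirm.
3. List change in viral load as a secondary endpoint.

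Two further changes are useful, but the correction does not depend on them:

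- Under the other analyses in SAP 6.1, state that viral load is analysed as Day 6 log10 load adjusted for baseline, with a rule for values below the detection limit (a censored-data model is one option). With 57.1% assumed undetectable in Arm 2 and 80.5% under the Arm 1 alternative, raw change would be limited by the assay floor.
- Reconcile the nasopharyngeal source in secondary endpoint 8 of 1.3.F with the oropharyngeal source in 1.1.A.

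The cost is wording in three protocol sections and one or two SAP sentences. The 60/60/30 design, the test and the power stay as they are, with no added patients, visits or assays.

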1.4 Preliminary Data

There is data supporting the antiviral activity of both hydroxychloroquine and azithromycin as single agents, but not much experience with the combination. In a recently completed trial [9] patients with COVID-19 (n=14) received hydroxychloroquine alone at the same dose and frequency proposed in this

Confirmed COVID-19

Protocol Version Date: 08-May-2020

study. For these patients, 8/14 had no detectable virus at day 6 by PCR quantification. In a smaller group of six patients receiving the combination of hydroxychloroquine and azithromycin at the doses and frequency proposed in this study, 6/6 had no detectable virus at day 6 by PCR quantification. It is this very preliminary, pilot observation in a very small number of patients that were not stratified or randomized that will be evaluated in this larger prospective randomized study.

1.5 Sample Size Justification

Randomized clinical trial comparing hydroxychloroquine with or without azithromycin in patients with the COVID-19 disease, with the addition of a third arm with a placebo and delayed hydroxychloroquine. Here we follow Gautret et al. [9] in using, as a primary endpoint, absence of viral evidence of disease six days following start of treatment. In that study (Table 3 of ref 9), there were 14 patients treated with hydroxychloroquine alone, and 8/14 (57.1 percent) of them were virus-free at 6 days. There were six patients treated with both hydroxychloroquine plus azithromycin, and all six (100%) were virus-free at 6 days. In a third group of patients with no hydroxychloroquine, there were 16 patients, of whom 2 (12.5 percent) were virus-free at 6 days. We propose a three-arm trial as follows: Arm 1 (HCQ + AZ), Arm 2 (HCQ alone), and Arm 3 (delayed HCQ), with patients randomized 2:2:1.

The primary outcome is a comparison of Arm 1 to Arm 2, with the aim of determining if the addition of AZ is effective. Using the proportion of patients that are virus-free at 6 days as the primary endpoint of the study, and assuming that the proportion of patients in the hydroxychloroquine arm who are virus free at 6 days is 0.571, the following table shows the detectable proportion virus-free in the combination arm with 80% power. These samples sizes are with a 5% level two-sided test of proportions.

Proportion virus-free HCQ only	Proportion virus-free HCQ plus AZ	Proportion difference	Patients per rm
0.571	0.821	0.250	52
0.571	0.805	0.234	60
0.571	0.771	0.200	85
0.571	0.721	0.150	158

For example, if we enroll 60 patients per arm, we could detect, with 80% power, an increase in the proportion of virus-free patients from 57.1% in the hydroxychloroquine arm to 80.5% in the combination arm.

The two-sided Type I error probability associated with this test is 0.05. We will use an uncorrected chisquared statistic to evaluate this null hypothesis.

A second, independent goal of the study is to ensure that, in fact, hydroxychloroquine is effective in reducing viral load. Thus, we plan a third, control arm, in which patients will receive a placebo for six days, at which time they will switch to receiving HCQ. We plan to compare Arms 2 and 3, with the control (Arm 3) having half the sample size of Arm 2. Based on the Gautret et al. study, we assume the baseline proportion of patients who are virus-free at six days is 0.125. The following table shows the detectable difference with a variety of baseline rates:

Proportion virus-free HCQ only	Proportion virus-free HCQ plus AZ	Proportion difference	Patients per rm
-----------------------------------	--------------------------------------	-----------------------	-----------------

ne for Treatment of

Confirmed COVID-19

Protocol Version Date: 08-May-2020

0.125	0.401	0.276	60
0.150	0.434	0.280	60
0.200	0.497	0.290	60
0.250	0.554	0.304	60

Thus, for a range of plausible virus-free rates for the control arm, the detectable rate for the HCQ arm is well within the range reported by Gautret et al. [9]. With this three-arm study, we will need 60 patients in each of the first two arms and 30 in the control arm, for 150 in total.

A key secondary endpoint will be the number of days from initiation of therapy to VND (virtually no disease). This can be displayed graphically using Kaplan-Meier survival curves, and formally assessed using a log-rank test. Other secondary endpoints that can be assessed in this way are (1) Time in days to being afebrile for 48 hours, (2) time in days to resolution of symptoms (as assessed by a symptom questionnaire), (3) time in days to discharge (if hospitalized), and (4) time to recovery (able to return to work or school). Other measures that will be assessed via descriptive statistics are agent toxicity and improvement over time in vital signs.

